3.5 CRITERIA FOR REMOVAL FROM PROTOCOL THERAPY AND OFF STUDY CRITERIA

Prior to removal from study, effort must be made to have all subjects complete a safety visit approximately 30 days following the last dose of study therapy.

3.5.1 Criteria for removal from protocol therapy

- Patients with medically concerning grade 3 or 4 adverse events related to drug therapy may be taken off therapy at the discretion of the principal investigator.
- Patients require more than 2 dose reductions of carfilzomib
- Toxicity has not resolved after 2 weeks of withholding treatment or up to 3 weeks for infection related treatment
- Grade 4 non-blistering rash or blistering rash of any grade
- Grade 4 neuropathy
- Grade 4 hypersensitivity reaction
- Patient completes the protocol as outlined in Section 3.2
- Progression of disease
- Patient chooses to go off therapy
- The principal investigator may remove patient from protocol therapy if deemed necessary due to medical conditions, compliance, etc.
- Patient becomes pregnant.

3.5.2 Off-Study Criteria

- Patient requests to be withdrawn from study
- Death
- Physician's determination that withdrawal is in the patient's best interest.
- Non-protocol therapy for myeloma; however, patients who have not progressed but choose to continue or resume lenalidomide maintenance beyond 32 cycles at an outside facility may stay on study at the discretion of the investigator.

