3.4 STUDY CALENDAR

Study	Pre-treatment	Induction Treatment							Extended Treatment				End of Treatment and Follow-Up	Disease Progression at any Time Point ^{l,p}
		Cycle 1					Cycle 2-8		Extended Dosing Phase (Phases I and II)				Every 3-6 months ^(j,p,r,s,t) or annual ^(v)	
		Day 1	Day 2	Day 8	Day 15	Day 22	Day 1 ^p	CR Achieved/End of Cycle 8 ^{m,n,o,p}	Day 1 of Cycles 9, 12, 15, 18, 21, 24, 27, 30 ^{c,e,r,s}	Day 1 Cycles 9, 12, 15, 18 ^{p,r,s}	Day 1 Cycles 9-32 ^{r,s}	Phase I-CR Achieved (Cycle 9-20)/ End of Cycle 20 and Phase II-CR achieved (Cycle 21-32)/ Treatment termination ^{m,n,o,p,r,s}		
Medical Record Review	x												x	
H&P	x	x	x	x	x	x	x		x					
ECOG	x						x		x					
Informed Consent	x													
Routine Labs ^a	x	x	x	x	x	x	x		x				x	x
Urine for UPEP and IFE ^m	x	x ^m					x ^m	x ^m	x ^m			x ^m	x	x
Viral Studies ^b	x													
Register for REMS®	x													
Pregnancy Test ^c	x ^c	x ^d	x ^d	x ^e	x ^e	x ^e	x ^c		x ^{c,e}		x ^{c,e}	x ^c	x ^e	
Myeloma Tests ^f	x						x		x			x ^q	x	x
Pharmacokinetic Studies		x ^k					x			x				
Research Blood/Urine	x		x	x	x		x	x	x			x ^r	x	x
Bone Marrow/Aspirate	x ^g		x ^h					x ^{i,o}				x ^{i,o}	x ⁱ	x
Skeletal Survey	x													
FDG PET-CT	x							x ⁿ				x ⁿ	x ⁿ	x
DW-MRI												x ^u		

the PI. In certain circumstances (at the discretion of the patient and PI), patients who are being followed by an outside oncologist and institution may continue to stay on study without a formal NIH visit, but by investigator-patient or investigator-physician phone or email communication to capture clinical and laboratory data. During the follow up phase, research blood/urine collection is optional and at the discretion of the PI.

- k. Pharmacokinetic studies Cycle 1 Day 1 will be collected at the following time points: pre-dose, end of infusion, 5, 15, and 30 minutes and 1, 1.5, 2, 4, 6, and 24 hours post administration for carfilzomib.
- l. At disease progression, marrow and FDG-PET/CT are optional.

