3.5.3 Off Protocol Therapy and Off-Study Procedure

Authorized staff must notify Central Registration Office (CRO) when a subject is taken off protocol therapy and when a subject is taken off-study. A Participant Status Updates Form from the web site (<http://home.ccr.cancer.gov/intra/eligibility/welcome.htm>) main page must be completed and sent via encrypted email to: NCI Central Registration Office [contact].

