5.1.4 Imaging

5.1.4.1 FDG-PET/CT

5.1.4.1.1 Schedule

FDG-PET scan will be performed on patients at baseline, during cycles 1-8 if patient obtains CR or at the end of cycle 8 if no CR obtained, during cycles 9-20 if patient obtains CR or at the end

of cycle 20 if no CR obtained, during cycles 21-32 if patient obtains CR or at treatment termination. During extension phase lenalidomide, FDG-PET scans are optional for those patients that are MRD negative at the end of cycle 8 regardless of response. Patients who remain on study will have PET scans performed on an approximate annual basis during the post-maintenance follow-up phase. At PI discretion, patient may be asked to have an additional PET-CT at progression.

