6.1.1 Long-term follow-up

When patients enter the long-term follow-up period, the following data will be collected:

- adverse events related to Carfilzomib
- survival status which will be collected by phone or clinic visit
- additional cancer therapy received

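### Section 3.5.2 takes patients off study at non-protocol myeloma therapy, and no legible text says survival is still collected afterwards; OS could be overstated to the extent that it is not

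*Combined protocol and SAP*

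**What the plan says.** Progression and off-study are separate events. Section 3.5.1 lists "Progression of disease" as a reason to stop protocol therapy. Section 3.5.2 does not list progression, but it does list starting other treatment: "Non-protocol therapy for myeloma; however, patients who have not progressed but choose to continue or resume lenalidomide maintenance beyond 32 cycles". The exception, which lets such patients remain on study while treated elsewhere, is at the investigator's discretion and covers only patients who have not progressed.

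On what follows, section 3.5.3 is administrative: "Authorized staff must notify Central Registration Office (CRO) when a subject is taken off protocol therapy and when a subject is taken off-study". Section 6.1 gives coming off study as one end point for adverse-event follow-up. In 5.1.4.1.1, annual imaging in follow-up is for those still on study: "Patients who remain on study will have PET scans performed on an approximate annual basis during the post-maintenance follow-up phase". The surviving part of calendar note j (section 3.4) says that some patients followed elsewhere "may continue to stay on study without a formal NIH visit, but by investigator-patient or investigator-physician phone or email communication".

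On survival, section 6.1.1 collects in long-term follow-up "survival status which will be collected by phone or clinic visit" and "additional cancer therapy received". Section 8.4 describes death from progression as an endpoint that the study captures. Section 6.3.6 defines OS from start of treatment to death from any cause. Section 10.3.2 plans Kaplan-Meier estimates with 95% confidence intervals and gives no censoring rule.

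**The concern.** The two groups of passages are not reconciled. For a patient who progresses and moves to next-line treatment, 3.5.2 ends study participation, while 6.1.1 expects survival and later therapy to be recorded. A study team could follow 3.5.2 and close the record at new therapy, or follow 6.1.1 and keep telephoning.

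The choice matters because next-line therapy usually follows progression. Closing the record there removes patients from the risk set when their mortality is likely to rise. Kaplan-Meier assumes that censored patients have the same future risk as those who remain. If they do worse, the curve is too high, and the reported confidence interval does not show it. OS is a stated secondary objective (1.1.2).

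**Working it through.** **Figures in the plan.** The documents give no OS rate, event count, follow-up length or OS precision target, so there is no OS figure to reproduce. The plan's toxicity figures do reproduce: P(5 or more of 45) is 7.29% at a true rate of 5% and 82.52% at 15% (stated 7.3% and 82.5%). They do not involve OS.

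**The path through the text.** Progression ends therapy (3.5.1). Non-protocol therapy ends study participation (3.5.2). The only stated next step is to notify the registration office (3.5.3). Section 6.1.1 gives survival collection no end date and does not say whether it covers off-study patients.

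**Size: worked example.** All rates are assumed. Take a median time to next therapy of 3 years, a death rate before it of d = 0.02 per year, and a median survival after it of 2 years.

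- a = ln 2 / 3 = 0.2310 and m = ln 2 / 2 = 0.3466 per year.
- True 5-year OS = exp(-(a+d)·5) + a·[exp(-5m) - exp(-5(a+d))]/(a+d-m) = 0.285 + 0.262 = 0.547.
- If everyone is censored at next therapy, only earlier deaths count, so Kaplan-Meier tends to exp(-0.02·5) = 0.905. The overstatement is 0.905 - 0.547, about 36 points.
- If half are censored there, simulation gives 0.665, about 12 points too high.

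**Size: scenario grid.** This adds a gap between progression and next therapy, which lets some deaths after progression be seen and so lowers the bias. Assumptions: median time to progression 3 or 5 years; median survival after progression 2, 3 or 4 years; death without progression 0.5% or 2% per year; exponential times; 7 years of follow-up; capture unrelated to prognosis; mean gap 0.15, 0.5 or 1.0 years. That is 12 scenarios for each gap. True 5-year OS runs from 55% to 80%.

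Overstatement of 5-year OS, in percentage points:

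| Survival captured after new therapy | Gap 0.15 y | Gap 0.5 y | Gap 1.0 y |
|---|---|---|---|
| 100% | 0 | 0 | 0 |
| 80% | 2-4 | 2-3 | 1-3 |
| 50% | 5-12 | 5-9 | 4-7 |
| 0% | 14-34 | 11-26 | 8-18 |

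At 3 years with no capture the figures are 6-17, 5-12 and 3-8 points. By 5 years, 32% to 65% of patients would have gone off study by this route. A separate set of assumptions, with median survival after next therapy as short as 1 year, gave 14-52 points at 5 years with no capture. The range therefore reflects the inputs and is not an estimate for this trial.

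**Direction.** With equal mortality before and after new therapy (0.10 per year), full follow-up and censoring agree: 60.7% and 60.7% at 5 years. If mortality halves after new therapy, the bias reverses: 66.2% with full follow-up against 60.7% with censoring.

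**Against sampling error.** For 45 fully followed patients the 95% half-width is 1.96·sqrt(p(1-p)/45): 14.5 points at p = 0.55 and 11.7 at p = 0.80. On the grid, the bias exceeds this only when fewer than about half are captured.

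**The case against.** A reader might infer that 3.5.2 by itself makes the trial's OS too high. The documents do not support that, for these reasons.

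- Neither 3.5.2 nor 3.5.3 says that survival collection stops.
- Section 6.1.1 asks for later cancer therapy, which for myeloma is normally the off-study trigger itself. Its list therefore reads most naturally as covering patients who have started such therapy. Section 8.4 points the same way, and 6.3.6 does not stop at new therapy.
- Section 6.1 names off-study as an end point for adverse-event follow-up, whereas 6.1.1 sets no such limit on survival. The imaging passage and note j do not concern vital status; note j shows that remote data capture was already accepted.
- Calendar notes a to i, the start of j and note v are not legible in the extract. Notes j and v govern the follow-up column and may settle the matter.
- Censoring at the date last known alive is the usual Kaplan-Meier convention. The missing sentence in 10.3.2 would on its own be only missing detail.
- Some patients may start other therapy while responding, for example a transplant with the cells harvested under 3.2.4. For them the bias could be nil or reversed.

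All of this stands, and it makes the consequence conditional. It does not remove the conflict. The exception in 3.5.2 allowing some patients to stay on study, the safety visit before removal from study (3.5) and the adverse-event limit in 6.1 all suggest that off-study ends participation. A team applying 3.5.2 as written could lose survival data that are hard to recover.

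**Conclusion.** The point holds in conditional form and is minor. The legible text does not reconcile off-study at non-protocol therapy with the evident intent to capture survival. OS would be overstated only if two things are both true: survival is not collected from a material share of patients after new therapy, and their mortality is then higher than before. The documents establish neither for this trial. Section 1.2.2 quotes a median survival of 6 months in patients refractory or resistant to bortezomib and at least one IMiD. That is a more advanced population, so it supports the direction and not the size.

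On the assumed rates the effect is negligible when capture is near complete, small at 80%, and comparable with or larger than the sampling error of 45 patients only when capture is about half or less. OS has no threshold or decision attached. The primary endpoint is scored in the first two cycles, so that analysis and the early stopping rule are untouched.

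**What to change.** 1. In 3.5.2 and 6.1.1, state that going off study for non-protocol therapy ends study procedures, but that survival status and next therapy continue to be collected by phone until death, withdrawal of consent or study close.
2. In 10.3.2, state that OS is censored at the date last known alive and not at the start of new therapy.
3. Report how many patients lack survival follow-up after new therapy, so that readers can judge any remaining bias.
4. For patients already off study for this reason, obtain vital status where consent allows.

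If the missing calendar notes already provide for this, a cross-reference from 3.5.2 and the censoring sentence in 10.3.2 are enough.

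The cost is a short clarifying amendment and continued phone contact, a route that 6.1.1 already names. No extra patients or study procedures are needed. Recovery for patients already off study depends on consent and may be incomplete, and the OS figure may become less favourable.

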3.5.3 Off Protocol Therapy and Off-Study Procedure

Authorized staff must notify Central Registration Office (CRO) when a subject is taken off protocol therapy and when a subject is taken off-study. A Participant Status Updates Form from the web site (<http://home.ccr.cancer.gov/intra/eligibility/welcome.htm>) main page must be completed and sent via encrypted email to: NCI Central Registration Office [contact].

4 CONCOMITANT MEDICATIONS/MEASURES

4.1 TUMOR LYSIS SYNDROME

4.1.1 Hydration and Fluid Monitoring:

- Oral hydration: All subjects must be well hydrated (i.e., volume replete). Begin oral hydration equal to approximately 30 mL/kg/day (~6–8 cups of liquid per day), starting 48 hours prior to the planned first dose of carfilzomib. Compliance must be reviewed with the subject and documented by the site personnel prior to initiating treatment with carfilzomib; treatment is to be delayed or withheld if oral hydration is not deemed to be satisfactory.

- IV hydration: 500 mL (250 mL before & 250 mL after carfilzomib) OR 1000 mL (500 mL before & 500 mL after carfilzomib) of normal saline or other appropriate IV fluid formulation must be given before *and* after each carfilzomib dose during Cycle 1 D1 and D2. Total volume will be determined at the discretion of clinician and volume status of patient. If lactate dehydrogenase (LDH) or uric acid is elevated at Cycle 2, Day 1, then the recommended IV hydration should be repeated for Cycle 2. The goal of the hydration program is to maintain robust urine output, (e.g., ≥ 2 L/day). Subjects should be monitored periodically during this period for evidence of fluid overload.
- In subjects considered to be still at risk for TLS at completion of Cycle 1, hydration should be continued into subsequent cycles if clinically indicated.

4.1.2 Laboratory Monitoring:

- Appropriate chemistries, including creatinine, and complete blood counts (CBC) with platelet count should be obtained and reviewed prior to carfilzomib dosing. Results of laboratory studies must be reviewed and deemed acceptable prior to administering the carfilzomib dose.
- Subjects with laboratory abnormalities consistent with lysis of tumor cells (e.g., serum creatinine $\geq 50\%$ increase, LDH ≥ 2 -fold increase, uric acid $\geq 50\%$ increase, phosphate $\geq 50\%$ increase, potassium $\geq 30\%$ increase, calcium $\geq 20\%$ decrease) prior to dosing should not receive the scheduled dose

4.1.3 Clinical Monitoring:

- Signs and symptoms indicative of TLS, such as fevers, chills/rigors, dyspnea, nausea, vomiting, muscle tetany, weakness, or cramping, seizures, and decreased urine output.
- Patients will be admitted to the inpatient hospital and observed while receiving Cycle 1 Days 1 and 2 of therapy.

4.1.4 Management:

- If TLS occurs, cardiac rhythm, fluid, and serial laboratory monitoring should be instituted. Correct electrolyte abnormalities, monitor renal function and fluid balance, and administer therapeutic and supportive care, including dialysis, as clinically indicated.
- All cases of TLS must be reported to Amgen as a Serious Adverse Event (SAE) through the normal process within 24 hours of the clinical site becoming aware of the event.

4.1.5 Optional medication for high risk TLS patients:

- Allopurinol is optional and will be prescribed at the Investigator's discretion. These subjects may receive allopurinol 300 mg PO BID (Cycle 1 Day -2, Day -1), continuing for 2 days after Cycle 1 Day 1 (total of 4 days), then reduce dose to 300 mg PO QD, continuing through Day 17 of Cycle 1. Allopurinol dose should be adjusted according to the package insert. Subjects who do not tolerate allopurinol should be discussed with the Lead Principal Investigator.

4.2 BONE DISEASE/EXTRAMEDULLARY DISEASE

4.2.1 Radiation Therapy

Subjects may receive radiation for treatment of uncontrolled pain, cord compression, vertebral instability/impending fracture, etc.

4.2.2 Kyphoplasty/Vertebroplasty

Subjects may receive kyphoplasty/vertebroplasty for symptomatic vertebral compression fractures.

4.2.3 Bisphosphonate Therapy

Approved bisphosphonate therapy (zoledronic acid or pamidronate) is allowed. Patients will be monitored for renal function and osteonecrosis of the jaw. Patients may require prior evaluation from dental specialist before instituting bisphosphonates.

4.3 HYPERCALCEMIA

Patients may receive treatment for hypercalcemia including hydration, bisphosphonates, furosemide, steroids, calcitonin, etc.

4.4 TRANSFUSIONS/GROWTH FACTORS

- Subjects may receive RBC or platelet transfusions if clinically indicated.
- Subjects may receive supportive care with erythropoietin or darbopoetin.
- Colony-stimulating factors may be used if neutropenia occurs but should not be given prophylactically.

4.5 ANTI-COAGULATION

Oral Aspirin 81 mg or 325 mg or suitable alternative anti-coagulation for thrombotic prophylaxis every day for the duration of their participation in the study.

4.6 HSV, VSV PROPHYLAXIS

Oral Valacyclovir of 500 mg daily or oral Acyclovir of 800 mg BID throughout all cycles in which carfilzomib is given.

5 BIOSPECIMEN COLLECTION

5.1 CORRELATIVE SAMPLES FOR RESEARCH/PHARMACOKINETIC STUDIES

NOTE: Effective with Amendment L (version date 07/15/2015), bone marrow aspirate and biopsy will be obtained for research studies at the discretion of the PI. Effective with Amendment N (version date 07/25/2017), samples for next generation sequencing (NGS) were added.

Correlate	Baseline	Day 2 Post 24 Hour Infusion	During Cycles 2-8 If CR achieved or End of Cycle 8	During Extended Dosing Phases (Phase I and II) if CR achieved during cycles 9-20/ End of cycle 20 and if CR achieved during cycles 21- 32/End of Cycle 32/treatment termination	Progression of disease
Pathology/IHC	X		X	X	X
Multiparametric Flow Cytometry	X		X	X	X
FISH/Cytogenetics (optional)	X				X
Molecular pathology for light or heavy chain immunoglobulin rearrangement and/or KRas and NRas mutation analysis	X		X (optional)	X (optional)	X
CD138+ Sorting/GEP Profiling/Microenvironment	X	X	X	X	X
Flow cytometry for proteasomes	X	X	X (optional)	X (optional)	X
Flow cytometry for autophagy	X	X	X	X	X
Other research labs as below including Next Generation Sequencing (NGS)	(Added with Amendment N; subjects beyond this cycle)			X	X
Storage	X	X	X	X	X

5.1.1 Bone Marrow and Peripheral Blood

- a. During extension phase lenalidomide, bone marrow biopsy and aspirates are optional for those patients that are MRD negative at the end of cycle 8 regardless of response.
- b. Patients may be asked to undergo bone marrow at progression of disease at the discretion of the PI.
- c. Collection of bone marrow, sorting of bone marrow and storage of bone marrow samples is

outlined in **Appendix B** and Section **5.2.1**.

- d. Correlative studies associated with bone marrow specimen will be performed and related to clinical outcome if the results of the study indicate a clinical or translational rationale for analyzing the samples. Such studies may include but are not limited to the following:
- i. Pathology/Immunohistochemistry: Bone marrow biopsy and aspirate will be sent to Clinical Center Department of Laboratory Medicine, Hematology Section for morphological evaluation by [name] and [name], PhD. Immunohistochemical staining will be performed under the direction of [name]. Plasma cell burden will be assessed using immunohistochemistry markers such as CD 138, light chains, CD56 etc. Plasma cells and microenvironment interactions will also be assessed using various immunohistochemistry markers for osteoblasts, osteoclasts, stromal cells and proteasomes.
 - ii. Minimal Residual Disease: Flow cytometry: Immunophenotyping of aberrant plasma cells by flow cytometry currently involves, but is not limited to, the use of the following reagents: CD138, CD19, CD45, CD38, and CD56. Characteristic changes in immunophenotypically abnormal plasma cells (CD138 positive) include but are not limited to absent CD19 and CD45, decreased CD38, and increased CD56. These studies will be performed under the direction of [name] of the flow cytometry unit in the NCI Laboratory of Pathology
 - iii. FISH and cytogenetics: Interphase FISH/cytogenetics will be performed on patients enrolled in this protocol under the direction of [name] of the Molecular Diagnostics Core Laboratory of the NCI Branch. (**NOTE:** [name] no longer at NIH/NCI, her involvement ended and these studies no longer being done as of Amendment M.)
 - iv. Myelomatous plasma cells will be studied at the single cell level by multiparametric flow cytometry for markers of autophagy, pre- and post-therapy, including but not limited to the technique described by S.T. Rosen *et al. J. Biol. Chem.* 284:26816-26830, 2009 under the direction of [name].
 - v. Flow cytometry for proteasomes under the direction of [name].
 - vi. Cell Sorting, GEP profiling, whole exome sequencing, microRNA analysis and microenvironment interactions - Marrow aspirate will be sent to the lab of [name] ([name]) in the Department of Laboratory Medicine and sorted into CD 138 + and CD 138 – fractions. [name] and [name] will also perform the below assays for unsorted bone marrow aspirate for VDJ sequencing and assessment of MRD negativity.
 - GEP profiling targeted exome sequencing, and VDJ sequencing for MRD assessment: Bone marrow aspirates will be collected and sent to the [name] Lab after 8 cycles of induction or CR, after 20 and 32 cycles of treatment and at annual follow-up milestones where BM aspirates are collected (if the samples were collected from the patients.) At baseline: CD138+ plasma cells will be purified from bone marrow aspirates harvested. Baseline CD138+ cells will be sent for VDJ sequencing and to Memorial Sloan Kettering ([name]) for targeted/whole exome sequencing and molecular expression analyses (depending on resources) in a coded, linked manner. At subsequent time points, once patient is in CR, plasma cells will not be purified and aspirates will be viably frozen. Samples will be sent out in batches. Of note, some samples

- may be sent to FDA/OHOP for next generation sequencing, see below .
- Bone marrow, blood and urine samples, and associated clinical lab data will be sent to Adaptive Biotechnologies Corp. for deep sequencing of the VDJ sequence. Samples and data will be submitted to Adaptive Biotechnologies Corp. in a coded, linked manner.
 - CD 138- fractions will be analyzed for microenvironment interactions such as cytokine profiling, miRNAs, etc. in the [name] Lab. A fraction of CD138- cells will also be cultured to isolate bone marrow stromal cells for further analyses. At the same time points, one 6 ml EDTA tube of peripheral blood will be collected for parallel analysis.
 - Both fractions will be collected, batched, and entered into a biobank. See Section 5.2.1 for storage of bone marrow biobank. As of Amendment N, aspirate samples will be stored in DLM under [name].
 - Aspirate samples may also undergo identification of downstream signaling targets, proteasome activity, and ubiquitination pathways on cell lysate or marrow aspirate.
- vii. Additional but optional molecular profiling including DNA-, RNA- and protein-based assays in bone marrow, blood, and urine samples will be performed. The purpose of these assays will be to further characterize underlying biology and correlate with clinical outcomes in an exploratory manner. These are not limited to, but include the following:
- Next Generation Sequencing (NGS) collaboration with Office of Hematology and Oncology Products (OHOP) FDA

This study will be included in the multi-protocol CCR collaborations with OHOP/FDA in terms of the translational and correlative aspects utilizing OHOP's "wet lab" to perform NGS assays on various human samples enrolled on a variety of CCR clinical trials. The transfer of samples will be performed under a CCR "umbrella" MTA. The samples will be locally biobanked in the BPC ([name] Lab) and batched at the NIH until time for shipment, at which time, the samples will be sent to:

ATTN: [name]
DBRR III/OBP/OPQ/CDER
Food and Drug Administration
[name],
[name],
[name] 20993
[contact]
Email: [contact]

The correlative NGS assays to be performed will be dependent on final agreement in investigating mutually important questions of interest with our collaborators. These include but are not limited to all or some of the following but are all optional:

1. T-cell receptor repertoire (immunoseq): More recently research in the literature has shown that patients most likely to benefit from immunotherapies are those who are found to have anti-tumor T cell clonality. Lenalidomide is an immunomodulatory and therefore it is important to analyze this along with immune subsets below in

SMM. NGS DNaseq will be used to analyze the VDJ sequence of T-cells to determine clonality. Input source may be PBMC or whole blood and approximately 2 ug of input gDNA will be needed which will amount to a whole blood collection of two 10 ml EDTA tubes. Collection time points include the following milestones, baseline, C8 or CR, 1 and 2 years, and during follow up phase.

2. Germline single nucleotide polymorphisms (SNP) and copy number variations (CNV) DNaseq: Whole exome or genome sequencing will be performed on peripheral blood to determine baseline germline SNPs and CNVs. Whole blood (one 10 mL EDTA tube) sample will be collected at baseline for germline DNA extraction. This DNA will be used to analyze and compare germline vs. somatic/tumor genetic alterations based on sequence data. Furthermore, germline normal polymorphic variation will be analyzed as genome-wide association study (GWAS) to determine whether certain normal variations predispose patients with treated SMM to progress to biochemical or overt symptomatic disease. Additionally, these germline variations may be analyzed for association with treatment related adverse events.
3. ctDNA: Targeted DNaseq will be performed on ctDNA for assessment of minimal residual disease (MRD). In addition to the VDJ targeted commercial assay to determine presence of the malignant clone, the library will also include other known recurrent genetic aberrations. Approximately 45% of myeloma patients have hyperdiploidy of one of the odd numbered chromosomes, the other 45% have specific translocations/deletions, well characterized, including translocations of 6;14, 11;14, 4;14, 14;16, 16;18, 17p del, and cMYC. Therefore, the assay will focus on both VDJ as with other hematologic malignancies and recurrent genetic alterations similar to the approach used in solid malignancies. Blood collection will involve two 10 mL EDTA tubes.
4. Gene expression profiling: RNAseq will be performed on CD138+ myeloma cells and correlated with DNaseq results. Additionally, peripheral blood/PBMC will be analyzed for immune related signatures. One 10 mL EDTA tube will be used for this purpose.

